A battery of assessments will be administered to assess mood, suicidality, and character traits. Ratings will be collected at multiple time points, including at baseline (2 hours), biweekly during medication treatment (1/2 hour), within one week of an MRI/PET scan (or at the conclusion of a mood-stabilizer trial), (1/2 hour), and at designated follow-up time points (2 hours). Patients may be video or audio-recorded with their consent during the administration of these scales.

IRB# 2012-1826-F PI: [name] Stony Brook University Human Subjects Committee (IRB) PSF 2/23/15

PSF 2/23/15 Page 22 of 37

Examples of measures that will obtained include:

- Hamilton Depression Rating Scale (15 min)
- Hamilton Anxiety Scale (15 min) (at baseline and repeat PET scan)
- Beck Depression Inventory (10 min)
- GAS (2 min) (administered by treating physician during clinical check-ins)

Data Analysis

PET data will be reconstructed into images using the appropriate software, coregistered to the MRI and regional time activity curves will be measured. The arterial input function will be used to derive the regional density of 5-HT transporters and 5-HT_{1A} receptors with kinetic modeling.

E. Statistics

Power Analyses

A power analysis was conducted to determine required sample size for detecting a difference in populations with 80% probability using a linear mixed-effect model with region and diagnosis as fixed effects and subject as random effect. This was accomplished by means of a simulation study for a variety of sample sizes. The noise level, the subject effect variance, and mean levels for each region were extracted from the linear mixed-effect model fitted to preliminary DASB studies. The diagnosis effect was taken from the 5-HTT data in bipolar disorder. To stabilize variance among regions, analysis will be performed on the log-transformed BP data. Results of the analysis indicate that 80% power will be achieved with 38 bipolar subjects and 38 controls and 10 unipolar subjects. Note that these results are for the simplest analysis – comparing bipolar patients with normal controls over six regions. If genotype or other covariates are found to have an effect, then including these factors in the model can be reasonably expected to control more of the variance and thus increase power of testing for a diagnosis effect.

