To assess the impact of lithium on the neuroreceptor measures we conservatively use the higher test/retest variability of the [¹¹C]DASB compound and assume a 20-25% change in both 5-HT_{1A} and 5-HTT after chronic lithium based on preclinical data. ¹4,16-18 Assuming 50% of the subjects complete the lithium treatment and repeat scans and this degree of change, we have a power of between 79% and 90% as this is a paired analysis. Estimated outcome measures will be analyzed for all ROIs and all patients in a linear mixed model with patient as random effect and ROI and remission status as fixed effects. Our previous studies have demonstrated that the standard deviation of BP across patients increases approximately linearly with the mean of the region, and so the BP values are first log-transformed in order to satisfy the assumptions of the modeling (constant variance across regions). For the pre/post imaging of the non-remitters, a linear mixed model will again be used with ROI and condition (before/after) as fixed effects and with two levels of random effects -- a patient effect and a study within patient effect. Many potential covariates will also be measured for each patient and will be included in the model when appropriate. Modeling will be done using R software (www.r-project.org).

F. Funding Status, Details

The study is currently funded through the National Institutes of Health (NIH) through May 31, 2017. Grant Title: Lithium's Molecular Mechanism of Action and the Pathology of Bipolar Disorder

G. Human Subjects Research Protection from Risk

1. Risk to Subjects and 2. Adequacy of Protection Against Risks

Risks associated with participation in this study are related to 1) Drug-free interval; 2) placement of intraarterial catheter; 3) blood sampling; 4) discomfort during scanning (PET and MRI); 5) MRI scan; 6) radiation exposure; 7) toxicology (idiosyncratic reaction to the tracer); 8) genetic testing/confidentiality; 9) pregnancy and 10) risks associated with lithium/lamotrigine use.

Stony Brook University Human Subjects Committee (IRB) PSF 2/23/15

Page 23 of 37

IRB# 2012-1826-F PI: [name] 1. Drug-free interval

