Official Title: PET and MRI Brain Imaging of Bipolar Disorder

NCT: NCT01880957

Document Date: 11/14/2017

Proposed Statistical Plan for [11C]-DASB (5-HTT) & [11C]-CUMI-101 (5-HT1A) from [name] **Bipolar Study**

Outcomes

DASB: V_T/f_p + bootstrap ROI error

CUMI: BP_F + bootstrap ROI error (BP_{ND}??)

A priori ROIs

DASB: acn, amy, midbrain, gcirc

CUMI: acn, amy, cin, dlPFC, parahippocampal gyrus, hippocampus, raphe

Statistical methods:

Linear mixed models with subject fit as random variable LMM also with DASB & CUMI reference regions and fp

Key outcomes: p-values for main effects/interactions; overall model R² & p-value; standardized & unstandardized β's, 95% CIs, p-values for post-hocs

Covariates

DASB: age

CUMI: age, sex, previous med status (dichotomous – w/n 4 years)

Post-Treatment

Sample: HC, pre BPD, post BPD

Question 1: Do post-treatment BPD levels of DASB or CUMI differ from pre-treatment levels and HCs?

Interactions of interest:

Group (relationship btw brain & Group across all regions) **Group*ROI** (ROI-specific relationship btw brain & Group)

Treatment Effects

Sample: pre/post BPD pairs

Tx response: % change in HDRS-24 (continuous) and remitter/non-remitter (dichotomous)

Question 2: Is the % change in DASB or CUMI associated with the treatment outcome?

Interactions of interest:

AHDRS (relationship btw brain & Tx outcome across all regions) **ΔHDRS*ROI** (ROI-specific relationship btw brain & Tx outcome)

Dichotomous

Interactions of interest:

Remission (relationship btw brain & Tx outcome across all regions)

Predicting Treatment Outcome

Sample: pre BPD with pre HDRS-24 + >7-week HDRS-24

Tx response: % change in HDRS-24 (continuous) and remitter/non-remitter (dichotomous) (responder ??)

Question 3: Do pre DASB or CUMI in any of the *a prioris* predict treatment response? Are the *a prioris* independent predictors of treatment response?

Interactions of interest:

PET roi (pre-treatment PET in ROI predicts treatment response)

Interactions of interest:

PET_roi (any significant ROIs are independent predictors of Tx response (over and above the other ROIs))

Same models fit with dichotomous remission status

Additional question: Do pre DASB & CUMI together predict more of the variance in treatment response than either method alone?

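### Baseline HDRS-24 is not a pre-specified covariate in the models relating PET to percent change and remission, so a PET–severity relation could bias the PET–response estimate in a direction that cannot be known in advance

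*SAP*

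**What the plan says.** In the SAP, Treatment Effects (Question 2) and Predicting Treatment Outcome (Question 3) both define response as the percentage "change in HDRS-24 (continuous) and remitter/non-remitter (dichotomous"). The Question 3 sample is "pre BPD with pre HDRS-24 + >7-week HDRS-24", so a baseline score exists for every patient analysed.

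The SAP's Covariates section gives age alone for DASB. For CUMI it reads "CUMI: age, sex, previous med status (dichotomous – w/n 4 years"). Baseline HDRS-24 is in neither list, and no model uses the follow-up score adjusted for baseline.

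The protocol's Statistics section (E) adds only this: "Many potential covariates will also be measured for each patient and will be included in the model when appropriate". That permits baseline adjustment but does not specify it.

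Neither document gives a baseline/follow-up HDRS-24 correlation, or a correlation of DASB or CUMI binding with baseline HDRS-24. The nearest statement is in protocol Section C.1. There the bipolar–control difference in 5-HTT binding, measured with the older tracer, is reported as independent of depression severity.

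**The concern.** Percent change has the baseline score as its denominator, and remission is usually a cut-off on the final score. Either can therefore depend on how ill the patient was at entry. If pre-treatment binding also varies with severity at entry, an unadjusted PET coefficient in Question 3 cannot separate prediction of response from tracking of initial severity. With at most 38 bipolar patients, a spurious predictor or a missed one is a realistic outcome. The score needed to separate the two is already required.

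Question 2 differs. Its listed terms are HDRS change and its interaction with region, which suggests that PET change is the dependent variable and HDRS change a predictor. There baseline severity matters as a possible confounder of two changes. The power argument for adjusting a clinical outcome does not carry over.

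**Working it through.** **1. The plan's own figures.** The documents state no power for the analyses relating PET to HDRS response. The group comparison has its own statement, "80% power will be achieved with 38 bipolar subjects and 38 controls". The nearest treatment figure is the paired PET analysis, with 79–90% power, on two assumptions: "Assuming 50% of the subjects complete the lithium treatment and repeat scans", and "assume a 20-25% change in both 5-HT_{1A} and 5-HTT after chronic lithium". That is 38 × 0.5 = 19 pairs. By normal approximation the implied SD of change is δ√n/(1.960 + z for power):

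- 20% change, 79% power: 0.20 × 4.359/(1.960 + 0.806) = 0.315
- 25% change, 90% power: 0.25 × 4.359/(1.960 + 1.282) = 0.336

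The two are close, so the range is plausible. The SD is not stated, so it cannot be verified, and it does not concern HDRS response.

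**2. When bias arises.** Let B be baseline, F follow-up and R = 100(F − B)/B. With PET and B standardised, the PET slope without B in the model is β + γc. Here β is the slope given baseline, γ is the effect of baseline on R given PET, and c is the PET–baseline correlation. Bias needs both γ and c to be non-zero.

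To first order, γ has the sign of ρ·SD(F)/SD(B) − mean(F)/mean(B), where ρ is the baseline/follow-up correlation. Baseline is 23.7 ± 6.3, rounded from protocol Table 1 (23.72 ± 6.27). Follow-up of 12 ± 8 is assumed. Then γ is zero when 8ρ/6.3 = 12/23.7 = 0.506, so ρ = 0.506 × 6.3/8 = 0.40. Below that value percent change is negatively related to baseline, and above it positively. The direction of bias therefore turns on two numbers that the documents do not give.

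**3. Simulation at n = 30 (Question 3).** Same inputs, with a PET residual correlation of 0.5 (assumed) and two-sided alpha 0.05. Unadjusted percent change is compared with follow-up score adjusted for baseline. Ranges show repeat runs.

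| ρ | PET–baseline | Power, unadjusted | Power, adjusted |
|---|---|---|---|
| 0.2 | +0.3 | 57% | 81% |
| 0.4 | +0.3 | 74% | 81% |
| 0.6 | +0.3 | 86% | 80–82% |
| 0.2 | −0.3 | 84–85% | 82% |

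With no true effect, at ρ = 0.6 and PET–baseline +0.3, the false-positive rate is 7.3–7.7% unadjusted and 5.0–5.5% adjusted. Over PET–baseline correlations of 0.3 to 0.5 in size, the unadjusted rate is about 5.5–12% and unadjusted power about 40–88%, against about 5% and 81% adjusted. A re-run at ρ = 0.2, 0.4 and 0.6 (10,000 trials per cell, dropping trials with any baseline at or below 5) agreed closely. Its lowest power was 38% at ρ = 0.2 with +0.5, and 32% at ρ = 0.6 with −0.5, so the lower end is approximate.

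**4. Other sample sizes.** A second simulation used 20,000 runs per cell, baseline truncated at 15, follow-up mean 55% of baseline with SD 7, and partial r = 0.45 (the last three assumed). With PET–baseline correlation 0.5:

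| ρ | n = 38: false positives | n = 38: power | n = 19: false positives | n = 19: power |
|---|---|---|---|---|
| 0.1 | 14% | 26% | 9% | 14% |
| 0.3 | 6% | 51% | 6% | 27% |
| 0.5 | 6% | 79% | 5% | 46% |
| 0.7 | 19% | 95% | 11% | 69% |

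Baseline-adjusted follow-up gives 5% false positives throughout, with power of about 82% (n = 38) or 48% (n = 19).

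With PET unrelated to baseline and n = 38, power unadjusted versus adjusted is 76 v 81%, 80 v 82%, 81 v 81% and 75 v 82% at the same four values of ρ. If response is proportional to baseline it is 83 v 80%, in favour of percent change.

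**5. Keeping percent change but adding baseline.** At n = 38 this also holds false positives at 5%, with power of 79–81% against 81–82% for adjusted follow-up. Under proportional response it is 82 v 80%.

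**6. Remission.** The SAP gives no cut-off. Assuming a final score of 10 or less, the inputs of step 3 and a linear probability test, false positives at PET–baseline 0.3 are about 8% (ρ = 0.4) and 12% (ρ = 0.6). At 0.5 they are about 13–14% and 23–25%. Adding baseline returns them to about 5%.

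**The case against.** The strongest case against is that the driving correlations are assumed, and the one related statement in the documents points the other way: Section C.1 reports a 5-HTT difference independent of severity. With PET unrelated to baseline, the whole issue shrinks to a few points of power, and to a small advantage for percent change if response is proportional to baseline. This stands as a limit on the size of the point. It does not settle it. The statement concerns a diagnosis contrast in 18 patients, with an older tracer and a different binding measure, and says nothing about CUMI.

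A second objection is that the protocol allows covariates when appropriate, and that percent change matches its own 50% improvement rule (Treatment Choice). Both are fair. Discretion after the data are seen is still not pre-specification, but the second argument is a good reason to keep percent change in the report.

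A reader might infer more than the documents support:

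- **That omitting baseline simply loses power.** It does not always. In some cells the unadjusted analysis shows higher apparent power, through bias.
- **That any PET–severity correlation must enter the estimate.** It does so only if the response measure also depends on baseline. Near ρ = 0.4 in step 2, percent change largely does not.
- **That these figures apply to Question 2.** The simulations take HDRS response as the outcome and pre-treatment PET as the predictor, so they do not.

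**Conclusion.** The omission is real and worth correcting, as a conditional bias of unpredictable direction. The SAP relates PET to percent change and to remission with no baseline HDRS-24 term, and the protocol's general wording does not supply one.

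The size in Question 3 depends on assumption. At n = 30, with a PET–baseline correlation of 0.3 to 0.5 in size, false positives for unadjusted percent change are about 5.5–12% rather than 5%. Power is anywhere from about 40%, or somewhat less, to 88% rather than about 81%. With no PET–baseline correlation the difference is a few points either way. The sample of 30, the follow-up distribution, the PET effect and both correlations are not in the documents; the baseline mean and SD are.

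For Question 2 the conclusion is qualitative: baseline severity is an uncontrolled possible confounder. Nothing here requires percent change to be dropped.

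**What to change.** **Question 3.** Name baseline HDRS-24 as a covariate in both the continuous and the remission models. Preferably make follow-up HDRS-24 the continuous outcome, with pre-treatment PET as predictor, and keep percent change, also baseline-adjusted, as a supporting analysis.

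**Question 2.** Add baseline HDRS-24 as a covariate, and state that the reason is confounding.

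**Cost.** The change is SAP wording, one degree of freedom per model, and no new data. If follow-up score is the outcome, the estimate is in HDRS points, which the supporting percent-change analysis offsets. If response is in truth proportional to baseline, the preferred model gives up about 3 points of power.

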After 6-10 weeks from the time of therapeutic or highest tolerable dose of treatment with either agent they will have repeat [\frac{11}{C}]CUMI-101 and [\frac{11}{C}]DASB PET scans. Blood levels of the lithium will be measured at the time of the repeat scan. At 6 weeks, if patients have not shown at least a 50% improvement in their HDRS score from the baseline interview they will be switched to lamotrigine. Similarly, if patients cannot tolerate treatment, they will be switched to lamotrigine and we will repeat both [\frac{11}{C}]CUMI-101 and [\frac{11}{C}]DASB scans 4-10 weeks after subjects are on therapeutic levels of lamotrigine. If subjects cannot tolerate either treatment, or if the subject scores a CGI-I (severity of illness) score of 4 ("moderately ill") or more after the week 4 visit for two visits in a row, and/or a CGI-II (global improvement) score of 6 ("much worse") or 7 ("very much worse") for 2 visits in a row, the subject will be considered a non-responder and will receive the repeat [\frac{11}{C}]CUMI-101 and [\frac{11}{C}]DASB scans. They will then receive open treatment in our clinic.

IRB# 2012-1826-F PI: [name] Stony Brook University Human Subjects Committee (IRB) PSF 2/23/15

PSF 2/23/15 Page 21 of 37

Neither lithium nor lamotrigine is approved by the FDA for acute treatment of depressive episodes in patients with bipolar disorder, and neither drug is approved for treatment of unipolar depression. Thus, the use of both drugs as treatment for depression in this study is off-label. Nevertheless, both drugs represent reasonable treatment options for depression which has failed to respond to traditional antidepressants in either bipolar or unipolar depressive disorders. There have been several reports of the efficacy of lithium and lamotrigine in both bipolar and unipolar depression (175-178). In this study, unipolar depressed patients will only be treated with lithium.

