Subjects will be offered up to 6 months of outpatient treatment and one month of medication at no cost. If the lithium or lamotrigine treatment is effective, it will be continued; if not, the subjects will be switched to open treatment with other drugs or other modalities. If subjects should still need additional treatment beyond the allotted time, they will be given referrals for continuing treatment elsewhere. In order to monitor renal and thyroid function, subjects taking lithium will have blood drawn (approximately 12.5 ml) for a comprehensive (14) metabolic panel, CBC with differential and Thyroid function tests (TSH and free T4) as well as an ECG after 3 months and 6 months from the start of treatment.

Clinical Monitoring

Personnel

Patients will be treated and monitored by psychiatrists in the Stony Brook Department of Psychiatry.

Frequency of clinical evaluations

For the initial 4 weeks of medication treatment, patients will see a psychiatrist in person at least once/week, and more frequently if clinical conditions warrant. If it is not possible to schedule an in-person visit every week, weekly phone contact may be substituted. Depending on each individual's clinical status, additional initial contact by the treating clinician may be either in person or by phone.

After 4 weeks, frequency of visits will be every two weeks up until the follow up PET scan, depending on combined evaluation of treatment response, and side effect issues. At minimum, all patients in active treatment will be seen monthly.

It should be noted that this outlines the minimum contact that each patient will have with their physician. In the course of the initial phases of treatment, patients may have multiple other contacts with clinically licensed personnel in the research program, such as psychologists, who will be involved in the conduct of this labor-intensive protocol. These staff members will be in frequent direct contact with treating physicians and will, therefore, constitute an extension of clinical monitoring.

Side effects

Side effects will be monitored in standard clinical fashion. MDs will interview patients about possible side effects at each contact and patients will be encouraged to call with any questions which may arise at any time. Response to side effects will depend on the circumstance. Doses may be titrated or patients may have medication discontinued, if clinically indicated.

Instruments

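### The SAP's 7-week HDRS-24 condition for Questions 3-4 can drop bipolar patients whom the protocol already calls non-responders, or score them on open treatment

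*SAP*

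**What the plan says.** The SAP section Predicting Treatment Outcome gives the Question 3 sample as "pre BPD with pre HDRS-24 + >7-week HDRS-24". Question 4 follows under the same heading with no other sample. The outcomes are percentage change in HDRS-24 and remitter status. Question 4 reports accuracy, AUC, sensitivity, specificity, NPV and PPV. The SAP does not say when week 7 starts, whether the later score must be on lithium or lamotrigine, or what happens to a patient stopped earlier. Question 2 has no week condition; its sample line is "Sample: pre/post BPD pairs".

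Protocol section D.5, Treatment Choice, gives three routes to non-responder status in one sentence. It opens "If subjects cannot tolerate either treatment, or if the subject scores" and continues with a CGI severity score of 4 or more at two visits in a row after the week 4 visit, and/or a CGI improvement score of 6 or 7 "for 2 visits in a row, the subject will be considered a non-responder and will receive the repeat" scans. The next sentence reads "They will then receive open treatment in our clinic". A later paragraph offers up to six months of outpatient treatment; effective treatment is continued and, "if not, the subjects will be switched to open treatment with other drugs or other modalities".

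Visits are at least weekly for the first four weeks, "and more frequently if clinical conditions warrant", with phone contact allowed as a substitute, and every two weeks after that. Under Instruments, ratings are taken "biweekly during medication treatment (1/2 hour), within one week of an MRI/PET scan (or at the conclusion of a mood-stabilizer trial").

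**The concern.** The protocol can declare treatment failure before the SAP will accept an outcome. A patient who worsens early and leaves study drug is an informative non-remitter for a model that predicts response from baseline PET. Under the SAP's sample rule that patient may have no qualifying score and disappear. Alternatively, the patient may have a qualifying score that reflects another drug, so that a remission on open treatment is credited to lithium or lamotrigine. The same rescanned patient can still count in Question 2.

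The consequences differ by analysis. In the continuous models, removing patients from the low end of the outcome can attenuate the slope and R². In the dichotomous models it removes non-remitters, which raises the remission share, so PPV rises and NPV falls.

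**Working it through.** The documents give no sample size, power or expected accuracy for Questions 3-4, so there is no planned figure to reproduce. The check has two parts: whether the routes can fire before week 7, and what a few exclusions would do.

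**Timing.** Take week 7 from treatment start (an assumption). The minimum visit schedule is weeks 1, 2, 3, 4, 6, 8, 10.

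- Intolerance: no minimum week. A lithium-intolerant patient is first switched to lamotrigine, so this needs early failure of both drugs, or of lamotrigine where lithium was not an option.
- CGI improvement 6-7 at two visits in a row: no minimum week on the natural reading. With biweekly ratings, the pairs (2,4) and (4,6) are met at weeks 4 and 6; with weekly CGI, the pair (1,2) is met at week 2. If the after-week-4 condition is read to govern this limb too, the first pair is (6,8), met at week 8.
- CGI severity of 4 or more: strictly after week 4 the first pair is (6,8), met at week 8. It is met at week 6 only if the week 4 visit counts or visits stay weekly.
- The week 6 switch to lamotrigine for less than 50% HDRS improvement is not a non-responder class and keeps the patient on study drug, so it is not counted here.

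If week 7 runs from target dose, lamotrigine reaches that dose at 2 + 2 = week 4, and the cut moves to 4 + 7 = week 11. Severity-route classifications at weeks 8 and 10 then also fall before it.

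**Size, dichotomous outcome.** The ceiling on the sample is the planned 38 bipolar patients (protocol D.3), so one patient is 1/38 = 2.6%. Assume 13 of 38 remit, sensitivity = specificity = 0.70, and k early non-remitters are dropped at random with respect to PET, leaving NR = 25 − k.

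PPV = (0.70 × 13)/(0.70 × 13 + 0.30 × NR) = 9.1/(9.1 + 0.3 NR)

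NPV = 0.70 NR/(0.70 NR + 0.30 × 13) = 0.7 NR/(0.7 NR + 3.9)

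| k | NR | PPV | NPV | Accuracy |
|---|---|---|---|---|
| 0 | 25 | 0.548 | 0.818 | 0.700 |
| 1 | 24 | 0.558 | 0.812 | 0.700 |
| 2 | 23 | 0.569 | 0.805 | 0.700 |
| 4 | 21 | 0.591 | 0.790 | 0.700 |

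With sensitivity 0.60 and specificity 0.80, accuracy goes from (7.8 + 20)/38 = 0.732 to (7.8 + 16.8)/34 = 0.724 for k = 4.

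**Size, continuous outcome.** Simulation with n = 38, an assumed PET-outcome correlation of 0.4, 40,000 replicates, dropping k patients:

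| k | Slope ratio, k worst outcomes dropped | Slope ratio, trigger correlated 0.7 with outcome |
|---|---|---|
| 1 | 0.91 | 0.95 |
| 2 | 0.84 | 0.92-0.93 |
| 4 | 0.75 | 0.88 |

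When the worst outcomes are dropped, mean sample R² falls from about 0.18 to 0.16, 0.15 and 0.14.

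**The case against.** The best defence is that the affected group may be very small. Early intolerance of both drugs is uncommon by construction. The worsening route has no pre-week-7 window if the after-week-4 condition covers it, and the severity route first fires at week 8 on the minimum schedule. A 7-week cut is also a sensible marker of an adequate trial: about one week of lithium titration plus the 6-week minimum before rescan. The illustrated effects are modest: at r = 0.4 and n = 38 the standard error of r is about (1 − 0.16)/√37 = 0.14, against a 12% slope loss of about 0.05. Nor is predicting response from baseline PET one of Aims 1-5; relating BP change to antidepressant effect (Aims 2 and 4) is Question 2, which has no week condition. All of this stands and limits the size. None of it supplies a rule for the patient who is stopped early.

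Four stronger readings are tempting and not supported.

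- A reader might infer that every early non-responder is either excluded or scored on open treatment. Repeat PET comes before open treatment and a rating falls within a week of a scan, so a patient classed at week 6 and scanned after week 7 can have a valid score.
- A reader might infer that the paragraph switching ineffective treatment to open treatment shows exits before week 7. It follows an offer of six months' care and names no week.
- A reader might infer that all the accuracy metrics are biased. The logistic slope, AUC, sensitivity and specificity shift only if the excluded patients differ in PET from other non-remitters.
- A reader might infer that worsening patients must wait for PET before rescue. The written order does not bar earlier care: Clinical Monitoring allows extra visits, and its side-effects paragraph allows discontinuation when clinically indicated.

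**Conclusion.** The concern holds in a limited form. As written, the Question 3-4 sample rule can select on the outcome being predicted, and it does not exclude HDRS-24 scores taken on open treatment. This is certain for intolerance, which has no minimum week, and holds for CGI worsening on the natural reading of the protocol sentence. The expected direction is attenuation of the continuous slope and R², higher PPV and lower NPV; accuracy changes little.

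The size is unknown because the documents give no count. The illustrated changes for four exclusions (PPV 0.55 to 0.59, NPV 0.82 to 0.79, slope down about 12% to 25%) rest on the assumed count, remission rate, sensitivity, specificity and correlation, and the 25% figure requires the four worst outcomes to be the ones lost. The change is worth making because the sample is small and the remedy uses ratings that the protocol already schedules.

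**What to change.** Change the SAP only.

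1. In the dichotomous Question 3-4 analyses, keep patients who meet the protocol's CGI non-responder rule as non-remitters, even without a score after week 7. Show intolerance stops both ways: counted as non-remitters and excluded.
2. Do not use any HDRS-24 taken after open treatment starts.
3. For the continuous outcome, add a sensitivity analysis using the last HDRS-24 on study drug.
4. State whether week 7 runs from treatment start or target dose, and report the number affected by route (worsening, severity, intolerance).

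The cost is a few lines of text. No new visit is needed, since ratings are already scheduled every two weeks and at the end of a mood-stabilizer trial, assuming the 24-item scale is used at those ratings. The one real judgement is how to treat intolerance, which is a tolerability event rather than an HDRS outcome; reporting both versions deals with it.

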Change in overall model R² from models with pre DASB & CUMI alone to combined model (If R² increases with both methods, tracers are predicting unique properties of Tx response)

Question 4: With what accuracy does pre DASB or CUMI predict treatment response?

Penalized logistic regression models

Additional question: With what accuracy do pre DASB & CUMI together predict treatment response Metrics of interest:

Accuracy, AUC, sensitivity, specificity, NPV, PPV, model factor importance ranking or % of variance explained with each factor

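### SAP Question 3 refits a mutually adjusted regional model for remission with no stated penalty; read as 7 CUMI regions plus 3 covariates it usually has no finite estimate near 19 patients and is unreliable up to about 30

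*SAP*

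**What the plan says.** The SAP lists the a priori regions as "DASB: acn, amy, midbrain, gcirc" (4 regions) and "CUMI: acn, amy, cin, dlPFC, parahippocampal gyrus, hippocampus, raphe" (7 regions). The covariates are age for DASB and, for the other tracer, "CUMI: age, sex, previous med status" (the last dichotomous).

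Under Predicting Treatment Outcome, Question 3 first asks whether baseline binding in each region predicts response. It then asks whether "any significant ROIs are independent predictors of Tx response (over and above the other ROIs"). The outcome is percentage change in HDRS-24, followed by "Same models fit with dichotomous remission status". A further item compares tracers by "Change in overall model R² from models with pre DASB & CUMI alone to combined model". The only mention of penalisation, "Penalized logistic regression models", stands under Question 4, which concerns accuracy.

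For Question 3 the SAP gives no model formula, sample size, expected number of remitters, or rule for collinearity or separation.

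**The concern.** Logistic regression has no finite maximum-likelihood estimate when some combination of the predictors splits remitters from non-remitters perfectly or almost perfectly. With many terms and few patients this happens by chance, and the reported coefficients and p-values then mean nothing. With 7 regions and 3 covariates there are 11 parameters including the intercept. If a quarter of patients remit, 38 patients give 38 × 0.25 = 9.5 remitters and 19 give 4.75.

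A second problem affects both outcomes. If regional values within a patient are strongly correlated, mutual adjustment widens every interval. A signal common to all regions may then appear as no region being an independent predictor, and a reader could take that for absence of prediction.

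**Working it through.** The plan states no figure for Question 3, so there is none to reproduce.

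**Inputs from the documents.**
- CUMI: 7 regions, 3 covariates. DASB: 4 regions, 1 covariate (SAP).
- Planned bipolar maximum: 38 (Protocol D.3, Study Sample).
- 38 × 0.5 = 19, from the protocol's assumption that half complete lithium and repeat scans (Protocol E, Power Analyses). It serves here only as a low point.

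**Assumptions.** The remission rate (50% down to 25%), the regional correlation and the prevalence of the binary covariates are not in the documents.

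**Step 1: exact formula.** For continuous predictors, no effect and 50% remission, Cover's count gives the probability that n patients with p predictors plus an intercept are separable:

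P = Σ(k = 0 to p) C(n−1, k) / 2^(n−1).

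For CUMI with covariates, p = 10. At n = 19, P = 0.5 + C(18,9)/2^19 + C(18,10)/2^18 = 0.5 + 0.093 + 0.167 = 0.76.

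**Step 2: simulation.** Remission labels are random and separation is tested by linear programming. The repeat run used 1,000 samples per setting, regional correlation 0.8, half the patients of each sex and 70% previously medicated.

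| n | Formula, 50% remission | Simulation, remission 50% to 25% | Repeat run, same range |
|---|---|---|---|
| 19 | 0.76 | 76-88% | 76-91% |
| 25 | 0.27 | not in this set | 25-63% |
| 30 | 0.07 | 6-34% | 6-36% |
| 38 | 0.004 | 0-12% | 0.5-12% |

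With no effect, correlation among regions does not alter these probabilities, because separability is unchanged by linear recombination of the predictors. A real effect raises them. With a log-odds of 1.0 per SD of mean binding, n = 38 and 30% remission, the figure is 13%.

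**Step 3: variants.**
- CUMI regions without covariates (p = 7): the formula gives 0.24 at n = 19. Simulation gives about 29-56% over the remission range (repeat run 25-51%). Both are near 0 at n = 38.
- DASB with age (p = 5): the formula gives 0.05 at n = 19, 0.003 at n = 25 and less than 0.001 beyond. In simulation at n = 19 it rises to 0.44 with 20% remission and a real effect.

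**Step 4: tests when estimates are finite.** For the CUMI model with covariates at n = 38, the likelihood-ratio test of a null region rejects about 11-12% at nominal 5% (repeat run 10.5-11.8%).

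**Step 5: collinearity.** With k = 7 equally correlated regions,

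VIF = (1 + (k−2)r) / ((1−r)(1 + (k−1)r)).

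This is 2.9, 4.3 and 8.6 at r = 0.7, 0.8 and 0.9, so standard errors are about 1.7 to 2.9 times larger.

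As an illustration, let the mean of the regions correlate 0.45 with percentage change, with r = 0.8 and n = 38. Each region's correlation with outcome is 0.45 × √(5.8/7) = 0.41, and its adjusted coefficient is 0.41/5.8 = 0.071. The standard error is about √((1 − 0.45²) × 4.31/27) = 0.36, with 38 − 11 = 27 residual degrees of freedom. The ratio is about 0.2, so power is close to the 5% chance rate. In simulation each adjusted region was significant in 5-6% of samples and a single mean score in 78-79%.

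**The case against.** The strongest reply is that the SAP does not write this model. The wording could mean that only regions significant one at a time enter jointly, which would leave fewer terms. The covariate list precedes the questions and does not say that it applies where binding is the predictor. Both points stand. The 7 + 3 model is therefore one reading of terse text, although the SAP offers nothing that rules it out. The two-step reading would add data-driven selection.

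A reader might infer that the remission model often fails across the whole range of 19 to 38 patients and with up to 11 regions. The documents do not support that:
- Question 3 needs a baseline scan and a later HDRS-24. It does not need a repeat scan or lithium, so 19 is not its sample. The true N is unknown. Dropout, patients with only one tracer (Protocol, PET Studies) and use of [18F]MeFWAY in place of CUMI (Protocol, Alternate Location and Tracer) all lower it below 38.
- At 38 patients separation is uncommon unless few remit.
- No 11-region remission model is written in Question 3. The combined-tracer item is defined through R² and comes after the line on remission. Combined accuracy falls under Question 4, where penalisation is named.
- DASB is largely unaffected.

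It is also fair that collinearity neither biases the continuous model nor invalidates its tests. The SAP lists 95% confidence intervals, so imprecision would be visible. To say that the question cannot be answered at all would go too far.

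**Conclusion.** The concern holds in limited form. An unpenalised remission model with 7 CUMI regions and 3 covariates is usually inestimable near 19 patients and unreliable up to about 30. At 38 it separates in 0-12% of null samples, but its likelihood-ratio test still rejects at roughly twice the nominal rate. These sizes rest on the all-regions-plus-covariates reading and on assumed remission rates.

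For the continuous outcome the issue is interpretation. Null adjusted coefficients are what a shared signal would produce under strong regional correlation, which is itself assumed. The protocol's earlier transporter data (C.1) make a shared pattern plausible: the bipolar deficit did not differ detectably across six regions (p = 0.247).

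This is a worthwhile and cheap correction to a secondary predictive question. It does not touch the group or pre/post comparisons.

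**What to change.** In the SAP, under Question 3:
1. Fit all remission models by Firth penalised likelihood, with profile penalised-likelihood confidence intervals and p-values.
2. State which regions and covariates enter the joint model and whether any prior screening applies.
3. Report N and the number of remitters for each tracer.
4. For both outcomes, add one pre-specified global score per tracer (the mean of the standardised log regional values) as the test of signal shared across regions. State that null mutually adjusted coefficients are not evidence against prediction.

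The score is an addition. Replacing the joint model by the score plus one region's deviation from it would change the question and would not cure collinearity. Under equal correlation the variance factor for the deviation is 7/(6(1−r)) = 3.9, 5.8 and 11.7 at r = 0.7, 0.8 and 0.9, against 2.9, 4.3 and 8.6 for full adjustment.

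Cost: a few sentences of SAP text and no new data. Firth estimates are shrunk, and there is one extra test per tracer for each outcome.
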